### 5. TREATMENT OF SUBJECTS

## 5.1 Subject Identification and Randomization

At screening, each subject will be assigned a unique three-digit subject number starting with 001. Numbers will be assigned by the study site personnel in ascending sequential order to each unique subject screened. If a subject is rescreened, the reason for rescreening will be noted and the subject will be assigned a new screening number. If a subject fails to be enrolled, the reason should be documented on the enrollment log. The subject will be considered a screen failure.

On Dosing Period 1/Day 1 subjects will be assigned a treatment sequence by a three digit randomization number starting with 101. The number is only for identifying a subject with their assigned treatment and not for subject identification.

# 5.2 Description of Study Drug

There are three study drugs: lasmiditan 200 mg oral tablet, lasmiditan 200 mg placebo oral tablet, and sumatriptan (lmitrex) 100 mg oral tablet. For purposes of the study all are referred to as study drug.

#### 5.3 Concomitant Medications

Use of any prescription medication, including MAO-A inhibitors and other drugs associated with serotonin syndrome, within 14 days prior to dosing (except hormonal contraceptives) except for 5-HT1 (serotonin) agonists and selective serotonin reuptake inhibitors which are restricted as noted in the table below. Any exceptions must be approved by the Investigator and Medical Monitor. Use of over-the-counter medications, including vitamins and herbal or dietary supplements within 7 days prior to dosing unless approved by the Investigator or designee and Medical Monitor. Acetaminophen for symptomatic relief of pain is allowed until 24 hours prior to dosing in each period.

Drug Class	Brands (examples provided)	Restricted prior to Day - 1 in all periods for:
5-HT1 (serotonin) agonists	Frova	6 weeks
Selective serotonin reuptake inhibitors (SSRI)/Serotonin norepinephrine reuptake inhibitors (SNRI)/tricyclic antidepressants (TCA)	Prozac	2.5 months
	Vivactil	3 weeks
Any other prescription medication(s)		14 days
Over-the-counter medications, including vitamins and herbal or dietary supplements		7 days

Prior medications are medications that were being taken within 30 days of signing the informed consent and finished prior to administration of the study drug. Concomitant medications are medications started prior to the start of the study and continued after

administration of study drug or started during the study after administration of study drug. Prior and concomitant medication use will be collected from Screening to EoS. It is not anticipated that the healthy volunteers participating in this study will be taking any prescription medications for any disorder.

If intake of a drug should become necessary for any reason during the course of the study, the subject is required to inform the Investigator or designee immediately. The Investigator or designee will record the drug, the dose, and the time of intake in the subject's CRF.

#### 5.4 Restrictions

### 5.4.1 Dietary and Fluid Restrictions

Subjects will fast for at least 10 hours prior to dosing and will continue to fast until at least 4 hours after dosing in each period. Meals during each dosing period will be standardized. All subjects will consume the same food during each meal. The composition of each meal may vary from day to day and between dosing periods. Subjects will fast at least 8 hours prior to any blood draw for clinical laboratory assessments.

The study drugs will be taken with 240 mL of water. Subjects will be allowed to drink non-sparkling water ad libitum, except for the time from 1 hour prior to dosing until 1 hour post-dose.

The consumption of grapefruit, grapefruit juice, Seville oranges, Seville orange juice, or beverages containing any of these juices or consumption of members of the mustard green family (including kale, broccoli, watercress, collard greens, kohlrabi, Brussels sprouts, and mustard (i.e. seeds, greens, spice or the condiment)) is prohibited within 72 hours of dosing.

The consumption of alcohol is prohibited beginning 72 hours prior to dosing (**Day 1**) in each dosing period until discharge from the unit. During all other times, the maximum intake of alcohol is limited to 1 unit per day (or 7 units per week; 1 unit of alcohol corresponds to 250 mL beer, 125 mL of wine, or 25 mL of spirits).

The consumption of tobacco is not allowed during the study.

Subjects are to refrain from consumption of caffeine-containing food or beverages (e.g. coffee, tea, cola, cocoa, chocolate) and of energy drinks for 72 hours before **Screening** and in each dosing period from 72 hours before each administration of the study drug until discharge (**Days -1** to **2**).

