#### **Study Endpoints**

**Primary Endpoint:** The pharmacodynamics of lasmiditan as measured by serial vital signs, ECGs, and AEs.

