### 6.5 Lasmiditan and Lasmiditan Placebo Administration

Double blinding will be accomplished as described in Section 5.6.

Investigational site staff will dispense lasmiditan 200 mg or its placebo according to the dosing plan. Lasmiditan will be co-administered with either sumatriptan (Imitrex) or lasmiditan placebo. The two study drugs will be swallowed simultaneously with 240 ml of water.

After dosing and rinsing with water, a hand and mouth check will be performed. Subjects will receive study drug in a sitting position on the bed. For the first 4 hours after each dose, the subjects will continue to fast and must remain seated on their bed at an angle of approximately 45° except to use the bathroom. They may then move freely within the Phase 1 unit per Institution policy, but should refrain from engaging in any strenuous activity throughout the study period.

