### 7. METHODS OF ASSESSMENT

So that data capture can be standardized, all assessments should be performed as indicated. In cases where blood sampling for PK analysis and other assessments (vital signs or ECGs) are scheduled to occur at the same time, the order of procedures will be: 5 minutes supine rest, ECG, supine vitals followed by standing vitals, and PK blood draw. This does not apply to screening procedures.

Every effort should be made to collect the PK samples at the exact times as specified (Table 2). Samples taken pre-dose and up to and including 8 hours post-dose will be taken ±5 minutes of the nominal time. Samples taken after 8 hours post-dose will be taken ±10 minutes of the nominal time.

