## 7.6 Vital Signs

Vital signs, measured after at least 5 minutes supine, will include supine systolic blood pressure (SBP), supine diastolic blood pressure (DBP), heart rate (HR), respiration rate (RR), and oral body temperature. All vital sign measurements will be performed by appropriately qualified and authorized study personnel, using appropriate equipment.

BP and HR will be measured if possible in the same arm at each visit by using automated devices. BP results will be recorded in millimeters of mercury (mmHg). HR will be measured in the humeral artery in the dominant arm for approximately 30 seconds and will be recorded as beats per minute (bpm). RR will be measured and recorded in breaths per minute. Oral body temperature will be measured in degrees Celsius.

At Screening and for interim and study exit vital signs, subjects who have a supine systolic BP > 135 mm Hg or < 90 mm Hg or who have a supine diastolic BP > 85 mm Hg or < 50 mm Hg will undergo at least one BP reassessment within 15 minutes of the original. Subjects who have a heart rate > 90 bpm or < 50 bpm will undergo at least one heart rate reassessment within 15 minutes of the original. All out of range results will be assessed by the PI, Sub-Investigator, or designee.

If interim BP or heart rate values are deemed clinically significant, subjects should be monitored by study staff and if deemed necessary from a safety standpoint, the patient will be discontinued.

Vital signs will be taken at Screening and at EoS. During each dosing period, they will be taken at check-in on Day -1, on Day 1 within 60 minutes of dosing and 1, 2, 4, and 8 hours after dosing, and on Day 2, 24 hours after dosing. Assessments will be performed at the nominal times +/- 15 minutes.

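### Menus may differ between periods and meal times are not fixed, which adds avoidable within-subject noise at 8 h, 24 h and in the later PK samples

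*Protocol*

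**What the plan says.** **Meals.** Protocol 5.4.1 standardises meals within each dosing period: "All subjects will consume the same food during each meal". The next sentence reads "The composition of each meal may vary from day to day and between dosing periods". Subjects "will continue to fast until at least 4 hours after dosing in each period". No clock time or post-dose time is given for any meal.

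**Readings.** The primary endpoint in the synopsis is "The pharmacodynamics of lasmiditan as measured by serial vital signs, ECGs, and AEs". SAP 4.1 keeps AEs and vital signs as PD endpoints and moves the rest to safety. Protocol 7.6 schedules vital signs "on Day 1 within 60 minutes of dosing and 1, 2, 4, and 8 hours after dosing, and on Day 2, 24 hours after dosing", and "Assessments will be performed at the nominal times +/- 15 minutes". Section 7.8 gives ECGs the same window. The VAS scales in 7.9.1–7.9.3 have ±20 minutes. DEQ-5 in 7.9.7 appears to have the same, although the tolerance there is printed only after the 24 h time.

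**Order.** When PK sampling coincides with ECGs or vital signs, Protocol section 7 says "the order of procedures will be: 5 minutes supine rest, ECG, supine vitals followed by standing vitals, and PK blood draw". VAS and DEQ-5 are not in this list. PK samples up to 8 h have ±5 minutes in Protocol Table 1 note 12, sections 7 and 7.13, and note 9 of the SAP's detailed schedule. Note 9 of Protocol Table 2 gives ±10 minutes.

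**Posture.** For the first 4 hours subjects "must remain seated on their bed at an angle of approximately 45° except to use the bathroom" (6.5, repeated in 6.7). Sections 7.6–7.8 require at least 5 minutes supine before each ECG and vital-sign reading, and 7.7 adds standing readings at 1 and 2 h.

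**Analysis.** Protocol 5.6 assigns seven subjects to each of six sequences. SAP 6.4.7 summarises vital signs descriptively by treatment and time point. Protocol 8.5 applies a paired t-test to log PK parameters. The model in SAP 6.4.9.2 has treatment as its only fixed effect.

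**The concern.** Each subject is their own control across three periods, so conditions that can be held constant between periods should be. The premise, which the documents do not quantify, is that blood pressure, heart rate and late drug concentrations can respond to what was eaten and how long ago.

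The plan lets one period's lunch differ from the next. It also lets the first meal fall anywhere from 4 h after dosing to shortly before the 8 h reading, and it does not say whether the 24 h reading comes before or after breakfast. The within-period baseline does not remove this, because it is taken before dosing, after the overnight fast.

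At stake is some precision in the treatment comparison at the later times. The 4 h subjective scales may also be taken before the meal in one period and after it in another.

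**Working it through.** **1. Figures in the plan.** The documents give no variability for vital signs or ECGs. The only statistical figure with stated inputs is the PK power: 36 completers, 25% within-subject CV, limits 80–125%, at least 80% power. With SD of the log difference = √(2·ln(1 + 0.25²)) = 0.348, 35 degrees of freedom and two one-sided 5% tests, power is 96.6% at a true ratio of 1.00, 89.5% at 0.95 and 76.3% at 0.92. The stated figure therefore holds for ratios of about 0.93 or nearer to 1. It makes no allowance for meals.

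**2. Which readings are exposed.** The fast ends no earlier than 4 h.

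| Measure | Post-dose times | Clearly after 4 h |
|---|---|---|
| Vital signs | 1, 2, 4, 8, 24 h | 2 of 5 |
| ECG | 1, 1.5, 2, 2.5, 4, 8, 24 h | 2 of 7 |
| PK | 14 samples, 0.25–30 h | 6 (6, 8, 12, 16, 24, 30 h) |

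**3. The 4 h ECG and vital signs.** In minutes after dosing, the vital-sign window alone is 225–255, so half of it lies after 240. But the PK draw comes last and is due by 245, with at least 5 minutes supine before the ECG. Supine rest must start by 245 − 5 = 240, before allowing any time for the ECG and vital signs themselves. The fast and the seated rule end at 240 at the earliest, which leaves 0 minutes for a meal or walking. With the ±10 minute window of Table 2 note 9, the limit is 250 − 5 = 245, which leaves at most 5 minutes.

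**4. The 4 h VAS and DEQ-5.** A ±20 minute window runs from 220 to 260. Up to 20 minutes lie after the earliest end of the fast, and no ordering rule applies.

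**5. Bias.** Each treatment is given in each period to 2 of 6 sequences × 7 = 14 subjects. A one-period effect therefore has weight (14 − 14)/42 = 0 in combination minus lasmiditan, and likewise in combination minus sumatriptan. If all 6 losses fell in one sequence, the largest weight in combination minus lasmiditan would be (14 − 8)/36 = 1/6. An assumed 5 mmHg effect would then shift that contrast by 0.83 mmHg.

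**6. Noise.** An effect *p* in one period adds +*p* to the paired difference in 2 of 6 sequences, −*p* in 2 of 6 and 0 in 2 of 6. Its mean is 0 and its variance (4/6)·*p*². Without a period term the SD is multiplied by √(σ² + (2/3)*p*²)/σ. Both *p* and σ are assumptions.

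| *p* (mmHg) | σ = 8 | σ = 10 | σ = 12 |
|---|---|---|---|
| 2 | +2.1% | +1.3% | +0.9% |
| 5 | +12.3% | +8.0% | +5.6% |
| 10 | +42.9% | +29.1% | +21.0% |

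**7. Posture.** Read literally, every supine reading from 1 to 2.5 h and every standing reading at 1 and 2 h breaks the 45° rule, whose only exception is the bathroom. At 4 h, that rule together with the ±5 minute PK window would allow supine rest to begin only at exactly 4 h 00.

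**The case against.** The strongest reply is that the design already deals with menus. Everyone eats the same food at each meal, so a change of menu is a period effect, and the sequences balance period over treatment. Vital signs and ECGs are only described, with no test, margin or power claim, so no formal conclusion depends on the extra variance. For PK, Protocol 1.2 reports that an earlier fed-versus-fasted study found a small food effect on lasmiditan. That study compared fed and fasted states rather than menus served later, but it gives no cause for alarm. All of this stands, and it is why the point is small. It does not answer the noise: balance removes bias from the mean but leaves the variance, and no planned analysis of these measures takes it out.

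A reader might infer more from the 4 h windows, namely that primary readings at 4 h could be fasted and rested in one period and post-meal and ambulant in another. The documents do not support that. Every ECG and vital-sign reading follows at least 5 minutes supine, and the order of procedures with the ±5 minute PK window leaves no time for a meal first. Nor do they support biased treatment contrasts, beyond a fraction under unbalanced dropout.

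On posture, it can be said that section 7 tells staff to perform assessments as indicated, so they know what to do. That is a fair reading, but the passages still contradict each other as written.

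**Conclusion.** The point holds as a cheap improvement of small size. Menus and meal times may differ between periods, the effect is noise rather than bias, and it reaches the 8 h and 24 h vital signs and ECGs and the six PK samples after 4 h. The 6–12% increase in the SD of paired differences is an illustration for an assumed 5 mmHg effect and an assumed SD of 8–12 mmHg. The documents supply neither input. The calculation also treats the effect as common to all subjects in a period, which follows from the same-food sentence; meal times that differ from subject to subject would not be covered by it.

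The 4 h ECG and vital signs are protected, though only by implication and provided the ±5 minute PK window applies. The 4 h VAS and DEQ-5 are not protected. They serve an exploratory endpoint, and SAP 6.4.10.5–6.4.10.6 summarise them by period as well as treatment, which would make a period difference visible but would not remove it.

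Two inconsistencies need reconciling whatever is decided on meals: the seated rule against the supine and standing readings, and the two PK windows. Table 2 note 9 may simply have lost a clause, since the SAP's parallel note gives both tolerances.

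**What to change.** - **Protocol 5.4.1:** replace the sentence allowing variation between periods with: *The same menu will be served at the same times after dosing in all three periods.*
- **Protocol section 7:** add: *All 4-hour assessments, including VAS and DEQ-5, will be completed before the first meal is served.*
- **Protocol 6.5 and 6.7 against 7.6–7.8:** reconcile the seated rule with the scheduled supine and standing assessments.
- **Protocol Table 2 note 9:** reconcile the PK tolerance with Table 1 note 12, sections 7 and 7.13, and the SAP schedule.

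The cost is a fixed unit menu and a first meal at most about 20 minutes later. Subjects are confined from Day -1 to Day 2 (Protocol 5.4.2), so the unit already controls what is served and when. Sample size and sampling times do not change.

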#### 5.4.2 Other Restrictions

Subjects will be confined to the Phase 1 unit for each dosing period from **Day -1 to Day 2.** Subjects will be discharged after the last assessment has been performed within that period (at least 30 hours post-dose for PK sample). In case of persisting adverse events, the subject may remain in the unit at the discretion of the Investigator or designee.

## 5.5 Treatment Compliance

Study medication will be administered in the Phase 1 unit under supervision. A mouth and hand check will be conducted for each subject after each dose to ensure compliance and proper ingestion.

# 5.6 Randomization and Blinding

This is a randomized, double-blind, three-period, cross-over, study to investigate the effect of single doses of sumatriptan (Imitrex) 100 mg on the pharmacodynamics of a single dose of lasmiditan 200 mg. The dosing periods are:

- A: Lasmiditan 200 mg co-administered with lasmiditan 200 mg placebo
- B: Sumatriptan (Imitrex) 100 mg co-administered with lasmiditan 200 mg placebo
- C: Lasmiditan 200 mg co-administered with sumatriptan (Imitrex) 100 mg

The study will be conducted at a single center. Subjects will be randomized using a Williams square design to one of six treatment sequences, as follows:

ABC	ACB
BAC	BCA
CAB	CBA

Seven of the planned 42 subjects will be included in each treatment sequence. The design is balanced for period and first order carryover effects.

Double-blinding will be accomplished as follows:

- Dosing staff, comprised of an unblinded pharmacist or designee (who prepared the medication), an unblinded dosing assistant, and an unblinded registered nurse (RN) will administer all study medications. They will have no other role in the trial and will not communicate their activities in the trial to other staff involved in the trial in any way.
- Investigational product, prepared in the Pharmacy by an unblinded Pharmacist
  or designee, will be dispensed from the Pharmacy in an amber medication vial
  (with a subject specific label blinded to the identity of the investigational
  product) to the unblinded dosing staff and dosed to the subject directly from the
  amber vial to the subject's mouth.
- Prior to dosing, each subject will be blind-folded and will remain blind-folded until the hand and mouth check has been completed. Curtains will be drawn around the bed prior to dosing and will remain in place until the hand and mouth check has been completed. No one will enter the curtained space other than the subject, the unblinded RN, and the unblinded dosing assistant.

## 6. STUDY DRUG MATERIAL AND MANAGMENT

#### 6.1 Lasmiditan

Lasmiditan drug product is a tablet containing 200 mg of lasmiditan (as free base). The tablet is white, film coated, and round with no markings. Lasmiditan drug product is for oral administration.

Lasmiditan hemisuccinate active pharmaceutical ingredient (API) was manufactured by Produits Chimiques Auxillaires et de Synthèse (PCAS), [name]. The drug product was manufactured by Patheon [name], or by Patheon [name] and contains the following inactive excipients: purified water, microcrystalline cellulose PH102, Starch 1500, sodium croscarmellose, sodium lauryl sulphate, magnesium stearate (non-bovine) and Opadry II White (film coating).

#### 6.2 Lasmiditan Placebo

Lasmiditan matching placebo contains purified water, microcrystalline cellulose PH102, Starch 1500, sodium croscarmellose, sodium lauryl sulphate, magnesium stearate (non-bovine) and Opadry II White (film coating). The placebo tablets match the active tablets in size, shape, and appearance.

Placebo was manufactured by Patheon [name], or by Patheon [name].

# 6.3 Lasmiditan and Lasmiditan Placebo Packaging and Labelling

Lasmiditan 200 mg matching placebo oral tablets will be delivered as bulk supplies in high-density polyethylene (HDPE) bottles from Catalent Pharma Solutions, Kansas City, Missouri, US.

All packaging and labeling will be performed according to Good Manufacturing Practice (GMP) and GCP rules. The lot number and date of manufacture for the clinical lot used in the study will be provided to the clinical site and will be reported in the Clinical Study Report. All study drug will be labeled with:

- Protocol number
- Sponsor's name and address
- Investigational New Drug statement
- Instructions for use and storage

# 6.4 Storage of Lasmiditan and Lasmiditan Placebo

All lasmiditan and its matching placebo should be stored by the study site at controlled room temperature of 25°C (77°F); excursions are permitted to +/- 15°C (59°F-104°F).

### 6.5 Lasmiditan and Lasmiditan Placebo Administration

Double blinding will be accomplished as described in Section 5.6.

Investigational site staff will dispense lasmiditan 200 mg or its placebo according to the dosing plan. Lasmiditan will be co-administered with either sumatriptan (Imitrex) or lasmiditan placebo. The two study drugs will be swallowed simultaneously with 240 ml of water.

After dosing and rinsing with water, a hand and mouth check will be performed. Subjects will receive study drug in a sitting position on the bed. For the first 4 hours after each dose, the subjects will continue to fast and must remain seated on their bed at an angle of approximately 45° except to use the bathroom. They may then move freely within the Phase 1 unit per Institution policy, but should refrain from engaging in any strenuous activity throughout the study period.

## 6.6 Sumatriptan (Imitrex)

Sumatriptan (Imitrex) 100 mg will be supplied by the Investigator (or designee) as tablets for oral administration. Branded Imitrex is planned to be used in this study. In the event that it becomes unavailable, a generic substitute may be used.

# 6.7 Sumatriptan (Imitrex) Administration

Investigational site staff will dispense sumatriptan (Imitrex) 100 mg according to the dosing plan. Sumatriptan (Imitrex) will be co-administered with either lasmiditan or lasmiditan placebo. The two study drugs will be swallowed simultaneously with 240 ml of water.

After dosing and rinsing with water, a hand and mouth check will be performed. Subjects will receive study drug in a sitting position on the bed. For the first 4 hours after each dose, the subjects will continue to fast and must remain seated on their bed at an angle of approximately 45° except to use the bathroom. They may then move freely within the Phase 1 unit per Institution policy but should refrain from engaging in any strenuous activity throughout the study period.

